## 2.4 Gradient- and Spin-Echo DSC perfusion imaging

The relative cerebral blood volume (rCBV), derived from dynamic susceptibility contrast magnetic resonance imaging (DSC-MRI), is an established biomarker of glioma status that can aid in diagnosis, detecting treatment response, guiding biopsies, and reliable differentiation of post-treatment radiation effects and tumor progression. It is also increasingly leveraged as a biomarker of early therapeutic response in clinical trials. A gradient-echo (GE) echo-planar imaging (EPI) sequence is commonly applied dynamically every 1-1.5 s, during which gadolinium-based contrast agent is injected as a bolus, and the T2\*-weighted images are used to calculate tumor blood volume (BV) maps.

The GE-EPI is more commonly used for DSC-MRI because it has high sensitivity to the susceptibility effect caused by the contrast agent. However, it also causes more susceptibility artifact in areas with tissue interface, hemorrhage and is more subject to the susceptibility-blooming near large vessels. When these factors are of concern, spin-echo (SE) EPI can be applied for DSC-MRI as an alternative approach in the clinic, despite its reduced overall sensitivity. In addition to their differences in overall sensitivity, it is well-known that GE-EPI is more sensitive to relaxivity changes caused by contrast agents in larger vessels whereas SE-EPI is more specific to those in vessels with size in the capillary level. When both GE and SE images are acquired following a bolus injection of contrast agent, a vessel size map can be constructed. The voxel value in the vessel size map represents mean vessel caliber of the voxel, which may serve as a useful surrogate for characterizing tumor angiogenesis and monitoring treatment-related changes.

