## 3.3 NUMBER OF PARTICIPANTS

Fifty (50) patients will be studied.

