## 5 Image Analysis

### 5.1 Metastasis size evaluation:

- 5.1.1 A patient must have a single enhancing intraaxial brain metastasis of 5 mm or greater for study inclusion.
- 5.1.2 Metastases will be measured on axial T1 post-contrast imaging on a slice displaying the maximal tumor size using the longest diameter after appropriate magnification on the picture archiving and communicating system (PACS) monitors.
- 5.1.3 Only metastasis planned for radiation therapy will be assessed (for example, lesions present at baseline imaging that are planned for surgical resection will not be assessed).
- 5.1.4 For patients with more than one metastasis appropriate for study assessment, up to ten (10) lesions will be assessed.
  - 5.1.4.1 If there are more than ten lesions present, the five most caudal (lowest) and the five most cranial (highest) lesions that meet evaluation criteria will be tracked.

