## 7.2 Sample Size

For each of the primary conspicuity endpoints, the objective is to estimate the ability of each imaging method (T2 weighted MRI, CEST MRI, Adv Diff, and DESE DSC) at identifying brain metastases at baseline. Standard of care qualitative T1 post-contrast imaging will be considered the gold standard. Each patient will have between 1 and 10 lesions, with an expected average of 4 lesions per patient. (For patients with more than 10 lesions, 10 will be chosen as described in Section 5.1.4.1.) The primary analysis will consider the largest lesion within each patient, and the analysis will be repeated considering all lesions. The sensitivity will be calculated along with the corresponding 95% confidence interval. With 50 patients, this confidence interval will be no wider than 14.5% on either side of the estimated proportion. The confidence interval around the proportion of total lesions detected will be tighter, depending on the total number of lesions.

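### With more than ten lesions, the ten tracked are chosen by height, which under-samples middle-ranked lesions and can omit the largest lesion that the primary analysis needs

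*Combined protocol and SAP*

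**What the plan says.** Section 5.1.4 sets a cap: "For patients with more than one metastasis appropriate for study assessment, up to ten (10) lesions will be assessed". Section 5.1.4.1 says how the cap is applied when it is exceeded: "the five most caudal (lowest) and the five most cranial (highest) lesions that meet evaluation criteria will be tracked". Section 7.2 takes the rule into the statistics: "For patients with more than 10 lesions, 10 will be chosen as described in Section 5.1.4.1". It also gives the planning figures: "Each patient will have between 1 and 10 lesions, with an expected average of 4 lesions per patient".

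The units of analysis are set in 7.2: "The primary analysis will consider the largest lesion within each patient, and the analysis will be repeated considering all lesions". Section 7.3 repeats this. It adds that the comparison of responders with local failures may be redone on all lesions if numbers permit.

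On location and image quality, section 2.4 says of gradient-echo echo-planar imaging that "it also causes more susceptibility artifact in areas with tissue interface, hemorrhage". It also mentions blooming near large vessels. It names no level of the brain.

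**The concern.** Two things are at stake.

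- **Representativeness.** In a patient with N > 10 eligible lesions, those ranked 6 to N-5 by height cannot be selected, and no analysis step corrects for this. The per-lesion results then describe a mix of lesions weighted towards the lowest and highest levels. The protocol itself says that one of the compared methods performs differently depending on local anatomy, so position is not obviously neutral for the all-lesion sensitivity or for the GESE-versus-GE difference.
- **The primary unit.** The primary analysis uses each patient's largest lesion, but size plays no part in the choice of the ten. In the patients with most lesions, the largest may not be tracked. The plan does not say whether the primary analysis would then use the largest of the ten or an additional, untracked lesion.

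**Working it through.** **Inputs from the documents:** 50 patients (3.3), a cap of ten lesions (5.1.4), selection by height (5.1.4.1), and a mean of 4 lesions with the largest as the primary unit (7.2, 7.3).

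**Not given, so assumed:** the distribution of lesion counts, the distribution of lesion heights, and any relation of size to height.

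**1. The plan's own figure.** Section 7.2 gives a 95% interval of at most 14.5% on either side with 50 patients. The exact (Clopper-Pearson) interval at 25/50 runs from 35.5% to 64.5%, a half-width of (64.5 - 35.5)/2 = 14.5%. The figure reproduces. It uses one lesion per patient, so the selection rule does not enter it.

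**2. How many patients are affected.** Write the lesion count as 1 plus a count with mean 3, to give the planned mean of 4. Then P(more than 10) = P(count of 10 or more).

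| Assumed count | P(N > 10) | Patients of 50 |
|---|---|---|
| Poisson | 0.0011 | about 0.1 |
| Negative binomial, k = 2 | 0.0302 | 1.5 |
| Negative binomial, k = 1 | 0.0563 | 2.8 |
| Negative binomial, k = 0.5 | 0.0829 | 4.1 |

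I use 0 to 5 patients as a rounded range. Planned lesions are 50 x 4 = 200. Two affected patients supply 2 x 10 = 20 (10%); five supply 50 (25%).

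**3. How far the ten depart from the patient's lesions.** I assume heights uniform from bottom to top, so the middle third holds 33% of lesions. Simulating the rule (100,000 draws per N) gives:

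| Lesions N | Share of tracked lesions in middle third | Chance that at least one tracked lesion is there |
|---|---|---|
| 11 | 29% | 97% |
| 12 | 25% | 94% |
| 15 | 14% | 72% |
| 20 | 4.7% | 30% |
| 30 | 0.3% | 2.5% |

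Under a random draw of ten, the expected share would be 33% in every row.

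**4. Effect on the all-lesion sensitivity.** Let w be the share of analysed lesions that comes from these patients. Let d be the difference in sensitivity between their ten tracked lesions and all their eligible lesions. The pooled estimate shifts by w x d: one tenth of d with two affected patients, one quarter of d with five. The documents give no basis for the size or sign of d.

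**5. Chance of missing the largest lesion.** If size is unrelated to height, this is (N-10)/N:

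- N = 11: 1/11 = 9%
- N = 15: 5/15 = 33%
- N = 20: 10/20 = 50%

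With five affected patients, the expected number whose largest lesion is untracked is 5 x 0.33 = 1.7 at N = 15 and 5 x 0.50 = 2.5 at N = 20. Replacing one patient's lesion by another changes the primary sensitivity by at most 1/50 = 2 percentage points, and only if the two lesions differ in detection.

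**The case against.** The rule has merits. It is fixed in advance, easy to apply, and leaves the reader little discretion. It touches only patients with more than ten lesions, possibly none. The primary analysis uses one lesion per patient, and the all-lesion work is secondary. GESE and GE are read on the same lesion region (5.6), so their comparison is paired: the lesion mix can change the size of a difference, but a gradient-echo artifact is a real property of that method. All of this stands and keeps the point minor. It does not justify choosing by height, because a seeded draw is equally fixed in advance.

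A reader might infer three stronger things, which the documents do not support:

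- **That the middle of the brain is never sampled.** The rule drops middle ranks, not a region. With 11 lesions it drops one. With 11 to 15, a mid-height lesion is usually still tracked under the uniform assumption.
- **That the lowest and highest levels are artifact-prone, so that the rule favours the spin-echo component.** Section 2.4 speaks of tissue interfaces, hemorrhage and large vessels, for gradient-echo imaging only. It ties none of them to a level, so a direction of bias cannot be claimed.
- **That the untracked share, 33% with 15 lesions or 50% with 20, measures the bias.** That share comes from the ten-lesion cap and would be the same under a random draw.

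It could also be said that the largest lesion would simply be read at baseline whether tracked or not. That is possible, but 5.1.4 limits assessment to ten lesions and 7.2 states no exception.

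**Conclusion.** The point holds as a minor design weakness with a cheap remedy. In patients with more than ten eligible lesions, selection by height under-represents middle-ranked lesions and over-represents the extremes. This could shift the all-lesion sensitivity, any all-lesion response analysis, and the size of the GESE-versus-GE difference. The direction is unknown. The overall size is probably small, because these patients are assumed to supply between none and a quarter of about 200 lesions.

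The link to the primary analysis is the more concrete part: 5.1.4.1 does not secure the lesion that 7.2 and 7.3 need. Under the same assumptions this concerns from none to about two or three of 50 patients. The stated 14.5% precision is unaffected.

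These sizes rest on assumed lesion counts, uniform heights, and size unrelated to height.

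**What to change.** Amend 5.1.4.1 so that, when more than ten eligible lesions are present at baseline:

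1. the largest eligible lesion is always tracked;
2. the other nine are drawn at random, with a pre-set seed, from the remaining N-1 eligible lesions;
3. the set is marked at baseline and kept for all later scans.

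A simple random draw of ten is not enough, since it misses the largest lesion with the same probability (N-10)/N. Nor is taking every k-th lesion: for 11 to 19 lesions, k = 2 yields only 5 to 10, and reaches ten only at N = 19 with one of the two starts.

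The largest lesion is then included with certainty and each other lesion with probability 9/(N-1). In 7.3, give the nine drawn lesions weight (N-1)/9, for example 10/9 = 1.11 with 11 lesions and 14/9 = 1.56 with 15, and the largest weight 1. Alternatively, report the all-lesion result with and without weighting. The weights sum to 1 + 9 x (N-1)/9 = N, so the patient counts as N lesions; multiply them all by 10/N if the patient should count as ten.

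The cost is a few sentences, a random list, and slightly harder re-identification of lesions at follow-up. No extra scans or readings are needed.

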### 5.2 Metastasis CNR evaluation:

- 5.2.1 The largest circular ROI that fits within the brain lesion on axial T1 post contrast imaging will be placed and will define the lesion ROI.
- 5.2.2 The ROI mean signal intensity will be recorded.
- 5.2.3 A mirror ROI will be placed in the contralateral normal appearing white matter and used as the “background” mean signal intensity measurement.
- 5.2.4 An extracranial ROI without visible artifact will be used as the “noise” mean signal intensity measurement.

### 5.3 Quantitative MRI

- 5.3.1 The largest circular ROI that fits within the brain lesion on axial T1 post contrast imaging will be placed and will define the lesion ROI.
- 5.3.2 The T1 and T2 tissue weighting that maximizes the ROI mean signal intensity will be identified.
- 5.3.3 A mirror ROI will be placed in the contralateral normal appearing white matter and used as the “background” mean signal intensity measurement.
- 5.3.4 An extracranial ROI without visible artifact will be used as the mean “noise” signal intensity measurement.

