## 1 OBJECTIVES

### 1.1 Primary Objectives

#### 1.1.1 Conspicuity:

- 1.1.1.1 Quantitative MRI: To assess the conspicuity of idealized T1 and T2 imaging at detecting brain metastases at baseline.
- 1.1.1.2 Chemical Exchange Saturation Transfer (CEST) MRI: To assess the conspicuity (CNR) of CEST imaging at detecting brain metastases at baseline.
- 1.1.1.3 Multiple B Value Diffusion Imaging (Adv Diff): To assess the conspicuity (CNR) of Adv Diff at detecting brain metastases at baseline.
- 1.1.1.4 Gradient- and Spin-Echo (GESE) Dynamic Susceptibility Contrast (DSC) perfusion imaging: To assess the conspicuity of GESE DSC and standard Gradient Echo (GE) DSC at detecting brain metastases at baseline.

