#### 1.2.2 Treatment Response:

- 1.2.2.1 Quantitative MRI: To assess the trend of idealized quantitative T1 and T2 values of brain metastases compared to normal brain parenchyma following treatment with stereotactic radiosurgery.
- 1.2.2.2 Chemical Exchange Saturation Transfer (CEST) MRI: To assess the ability of CEST imaging to differentiate radiation necrosis from progressive disease in brain metastases following stereotactic radiosurgery.

- 1.2.2.3 Multiple B Value Diffusion Imaging (Adv Diff): To assess whether Adv Diff can differentiate radiation necrosis from progressive disease in brain metastases following stereotactic radiosurgery.
- 1.2.2.4 Gradient- and Spin-Echo DSC perfusion imaging: To assess whether GESE DSC improves differentiation of radiation necrosis from progressive disease in brain metastases following stereotactic radiosurgery compared to standard GE DSC.
- 1.2.2.5 Multiple inversion time (TI) arterial spin labeling (ASL) “Adv ASL” perfusion imaging: To assess the ability of Adv ASL to differentiate radiation necrosis from progressive disease in brain metastases following stereotactic radiosurgery.

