Recent developments in rapid multi-parameter mapping techniques are possible due to advances in accelerated imaging and reconstruction techniques. These typically incorporate efficient pulse sequence designs and mathematical constraints to assess the desired information in each pixel. SyntheticMR developed the first clinically available method and released by GE Healthcare as "MAGIC" (MAGnetic resonance Image Compilation), which can achieve whole brain quantitation in 5-6 minutes. The SyntheticMR method assumes the process of T1 and T2 relaxation times to be monoexponential, whereas it may be multi-exponential for many tissues. However, a phantom study has revealed good accuracy and reproducibility for T1, T2, and PD measurements by the SyntheticMR method. These measured parameters can also be applied to an MR spin model produce images with almost any contrast weighting by virtually changing repetition time (TR), echo time (TE), and inversion time (TI). Synthetic MRI is particularly useful when many different contrast settings (for example, T1 weighted imaging (WI), T2WI, proton density WI) are required. Synthetic MRI of the brain without the use of a contrast agent has been reported to produce images that although inferior in image quality the diagnostic power of the images was comparable to that of images obtained via conventional MRI sequences. Therefore, if the diagnostic power of images obtained via synthetic MRI after administration of a contrast agent is also proved to be comparable to that of conventional MRI, synthetic MRI could

be a useful means of screening for brain metastases, significantly reducing scan time and providing quantitative data.

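### Section 5.3.2 chooses the quantitative-MRI weighting by lesion brightness rather than lesion-to-background contrast, and no TR/TE/TI range is stated for the search

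*Combined protocol and SAP*

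**What the plan says.** Primary objective 1.1.1.1 reads: "To assess the conspicuity of idealized T1 and T2 imaging at detecting brain metastases at baseline". Its neighbour for CEST spells out what conspicuity means: "To assess the conspicuity (CNR) of CEST imaging at detecting brain metastases at baseline". The Adv Diff objective carries the same CNR label.

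Section 5.3 sets the procedure in four items. Item 5.3.1 defines the lesion ROI. Item 5.3.2 is the only selection rule in the document: "The T1 and T2 tissue weighting that maximizes the ROI mean signal intensity will be identified". The reference readings come afterwards: "A mirror ROI will be placed in the contralateral normal appearing white matter" (5.3.3), and "An extracranial ROI without visible artifact will be used as the mean" noise reading (5.3.4).

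Section 2.2 says the measured parameters can be turned into "images with almost any contrast weighting by virtually changing repetition time (TR), echo time (TE), and inversion time (TI"). No section gives a range, grid or fixed setting for any of the three. Sections 7.2 and 7.3 add no selection rule. Section 7.3 calls for CNR by imaging method and time point, compared between responding and failing lesions.

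**The concern.** A lesion is conspicuous when it differs from its surroundings, not when it is bright. A setting that brightens the lesion may brighten white matter as much or more. The plan collects both readings needed for a CNR, but uses them only after the image has been chosen without them.

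The missing range makes this worse. If lesion signal has no interior maximum in TR and TE, the search ends at the edge of whatever the software or analyst allows. The image scored as idealized would then be set by limits that nobody wrote down, and it need not be the image that shows the lesion best. What is at stake is the quality and reproducibility of the quantitative-MRI conspicuity measure at baseline.

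**Working it through.** **The plan's own figure.** Section 7.2 gives 14.5% on either side for 50 patients. The exact (Clopper-Pearson) 95% interval at 25/50 is 35.5% to 64.5%, a half-width of 14.47%. The figure is reproduced. It depends only on n = 50, so this point does not touch it.

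**Model (assumed).** Section 2.2 states: "The SyntheticMR method assumes the process of T1 and T2 relaxation times to be monoexponential". On that basis take a spin-echo signal

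S = PD × (1 − exp(−TR/T1)) × exp(−TE/T2).

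For any lesion, S rises with TR and falls with TE. Its maximum over a TR/TE box is always at the longest TR and shortest TE, whatever the lesion's T1 or T2.

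**Inputs (all assumed; the documents give none).** White matter: PD 0.70, T1 850 ms, T2 70 ms. Twelve lesions: PD 0.72, 0.78 or 0.85; T1 500 or 1500 ms; T2 100 or 130 ms. T1 and T2 images are searched separately, with noise equal across weightings. Contrast = lesion S − white-matter S. Ratio = largest |contrast| in the range ÷ |contrast| where lesion signal is greatest.

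**One case in full.** Lesion PD 0.72, T1 500, T2 100; range TR 2000–8000, TE 40–200.
- Rule's pick, TR 8000 / TE 40: lesion 0.4826, white matter 0.3953, contrast 0.087.
- Best contrast, TR 2000 / TE 58: lesion 0.3957, white matter 0.2766, contrast 0.119.
- Ratio 0.1191 / 0.0874 = 1.36.

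**All 12 lesions.**

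| Range (ms) | Rule's pick, every lesion (TR/TE) | Median ratio | Range of ratio | Lesions at 1.2 or more |
|---|---|---|---|---|
| Narrow T1w: TR 300–800, TE 10–20 | 800/10 | 1.00 | 1.00–1.07 | 0 |
| Narrow T2w: TR 3000–8000, TE 80–120 | 8000/80 | 1.01 | 1.00–1.06 | 0 |
| Wider T1w: TR 300–1500, TE 10–30 | 1500/10 | 1.25 | 1.08–1.54 for 10 lesions | 7 |
| Wider T2w: TR 2000–8000, TE 40–200 | 8000/40 | 1.16 | 1.00–1.36 | 5 |

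In the wider T1w range the other two lesions have almost no contrast under the rule (−0.017 and −0.005), so their ratios are not used as a range end.

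**Sensitivity to the assumptions.**
- Over 27 white-matter settings (PD 0.65–0.75, T1 750–950, T2 60–80) the medians run 1.00–1.04, 1.00–1.06, 1.20–1.47 and 1.06–1.42, in table order.
- With an inversion-recovery magnitude model (TR 2500, TE 10), the rule goes to an end of the TI range for every lesion. The median is 1.02 (at most 1.28) for TI 500–900, and 1.16 (1.03–2.03) for TI 300–1200.
- If noise scaled with white-matter signal, the medians would be 1.60, 1.63, 2.84 and 6.66, in table order.

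**The 7.3 comparison.** Twelve lesions give 12 × 11 / 2 = 66 pairs. Moving from the current rule to lesion-by-lesion contrast tuning shrinks the between-lesion gap in 30 of 66 pairs in the wider T2w range. Comparing absolute contrasts in the wider T1w range, 39 of 66 gaps shrink. Raising each lesion's own contrast therefore does not reliably separate lesions from one another.

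**The case against.** The best case for leaving 5.3.2 alone has five parts.

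- **No stated result is shown to suffer.** A reader might infer that primary sensitivity is understated. The documents do not support that: no passage links CNR to a lesion counting as detected. Nor does any passage say that the image identified in 5.3.2 is the only one scored. This stands.
- **A reader might infer a loss of power in 7.3.** In the wider T2w range the rule picks TE 40, where the gap factor between T2 100 and T2 130 lesions, exp(−TE/130) − exp(−TE/100), is 0.0648. At TE 80 it is 0.0911, about 1.4 times larger. But a contrast rule would not settle on TE 80 for every lesion, and the pair counts above go both ways. The between-lesion spread is also not given, so power cannot be computed. This stands.
- **With sensible limits the loss is trivial.** True for the narrow ranges, where it is at most 7%. But no limits are written, so the reader cannot tell which case applies.
- **A CNR rule can also run to an edge.** With noise proportional to white-matter signal, it goes to the longest TE in both T2w ranges. This stands, and it means that the range must be stated under either rule.
- **Tuning makes images differ by lesion.** In the spin-echo model the current rule gives all lesions the same image. A contrast rule does not, and a lesion can even switch from dark to bright: in the wider T1w range one goes from −0.005 to +0.049. This stands, and it is why 7.3 needs a common weighting.

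The trend of T1 and T2 values in objective 1.2.2.1 ("To assess the trend of idealized quantitative T1 and T2 values of brain metastases compared to normal brain parenchyma") might also seem affected. It concerns the measured values themselves and need not depend on 5.3.2.

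**Conclusion.** The text establishes two things: the selection rule targets lesion signal although the objective is conspicuity, and the search range is unstated. In a monoexponential spin-echo model it follows that the range limits, not the lesion, determine the image.

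The size depends wholly on assumed tissue values, ranges and equal noise. Best available contrast exceeds contrast under the rule by at most 7% with narrow ranges, and by a median of 25% (T1w) or 16% (T2w) with the wider ones tried. The documents cannot say which applies.

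This is a cheap improvement of minor weight to the baseline conspicuity measure. It changes neither the sample size nor the 14.5% precision, and no benefit is claimed for the primary sensitivity or for the 7.3 tests.

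**What to change.** Replace 5.3.2 with wording such as: *For the T1 image and the T2 image separately, select the weighting that maximises |lesion ROI mean − contralateral white matter ROI mean| / noise (5.3.3, 5.3.4), over a TR/TE/TI range stated before analysis and identical for all patients and time points. Report the weighting chosen, and state that it was tuned on the lesion being scored.*

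Add to 7.3: *CNR comparisons between lesion groups and across time points use one common weighting for all lesions.*

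The cost is a few sentences and some offline reprocessing of synthetic images. The ROIs are already collected, and no scan time or patients are added.

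There are two downsides, both in the baseline conspicuity measure. First, tuning flatters contrast slightly. With an assumed 3% or 5% random error in lesion PD, T1 and T2, observed contrast exceeds true contrast by 1.2% or 3.3% in the wider T1w range, against 0.7% or 2.3% under the current rule. In the other three ranges the excess is under 1%. Second, the weighting can differ by lesion, which is why it should be reported.
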